7.4 Risks/Benefits Analysis

The principal risks to participants are intensive statin therapy, exposure to ionizing radiation as part of the coronary CT angiogram, receipt of iodinated contrast and receipt of gadolinium based contrast. As noted in 7.3, above, large clinical trials have demonstrated low rates of significant adverse events due to statins, few if any of which persist after drug discontinuation. The study population has been specifically selected to be at the lowest risk for ionizing radiation, and the CT protocol carefully tailored to ensure delivery of the lowest possible dosage necessary to generate diagnostic images. The limitation of enrollment to patients with GFR > renders the risk of iodinated and gadolinium based contrast negligible.

The level of risk to the research participants was initially determined to be greater than minimal risk (45 CFR 46 102). As of January 2017, the study status of this protocol changed to "data analysis only" and the level of risk of this study is now minimal.

This research involves the prospect of direct benefit to individual subjects through potential identification of clinically silent atherosclerotic disease and according intensification of statin therapy that would not otherwise be indicated in usual clinical care. This carries the likelihood of significant reduction (16-21% relative risk reduction) of the risk of clinical cardiovascular events.⁴⁷

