1.0 Introduction

1.1 Study Objectives:

The purpose of this study is to evaluate the hypothesis that use of atherosclerosis imaging to set targets for cholesterol lowering therapy will result in greater regression of atherosclerosis than standard therapy.

The primary efficacy endpoint of this study is the wall volume of the internal carotid arteries as measured by magnetic resonance imaging.

Secondary endpoints are

- A. Arterial stenosis and plaque volume measured by coronary MDCTA
- B. Dosage of statin medications required to achieve LDL targets.
- C. Combined incidence of stroke, nonfatal MI, myocardial revascularization, hospitalization for unstable angina or heart failure and death.
- D. FDG plaque uptake within the carotid and coronary arteries.

E. Reproducibility of arterial stenosis and plaque volume measured by MDCTA.

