It is widely postulated in the literature that ¹⁸F-fluorodeoxyglucose (FDG) imaging can improve risk assessment and prognostication through the identification of high-risk "vulnerable" plaques, plaques that demonstrate heightened inflammation, neovascularization or apoptosis. The primary target is the carotid and coronary arteries, imaging will also include the ascending and descending aorta, and the iliac arteries. Successful FDG PET imaging has been performed in large vascular beds, including the carotid arteries, and recent preliminary reports suggest the potential for noninvasive coronary plaque imaging. The advantage of nuclear imaging is that multiple vascular beds can be imaged with a single radionuclear isotope administration.

In a subset of 60 individuals we plan to study the reproducibility of arterial stenosis and plaque volume as measured by MDCTA.

At present, there is no available data on the reproducibility of 320 detector row MDCT for measuring arterial stenosis and plaque volume. This data will allow investigators to determine whether measured changes in stenoses and plaque morphology exceed that expected from the limits of measurement error in CTA and thus make the results of ongoing trials more reliable.

Consistent with such objectives, our specific aims are:

1st Aim

To examine whether image guided lipid lowering therapy is superior to NCEP guided therapy in promoting carotid atherosclerotic plaque regression and stabilization.

2rd Aim

To investigate whether the observed change in carotid atherosclerosis volume measured by MR, parallels observed change in coronary atherosclerosis volume measured by MDCT angiography.

3rd Aim

To examine whether MRI guided plaque regression and stabilization produces greater reduction in clinical CV events than standard NCEP guided therapy.

4th Aim

To examine the statin dosages required to promote plaque regression and stabilization differ between conventional and image guided strategies.

5th Aim

To investigate whether FDG PET activity predicts carotid morphological plaque regression and stabilization in both the carotid and coronary arteries and compare the efficacy of PET based prediction with MRI.

6th Aim

To correlate FDG uptake in the carotid, coronary, aortic, and iliac arteries with absolute values and changes in hematological biomarkers of vascular inflammation, thrombosis and atheroprotection at and between each time point.

7th Aim

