traditional risk-factor based care). This hypothesis will be tested in a study in which subjects are entered and then followed until either (a) the terminal event occurs, or (b) they drop out of the study, or (c) the study ends and the patient is censored while still being actively followed. The study design calls for an accrual period of 50 months and a follow-up period of 24 months. Computation of power for this analysis is based on a hazard ratio of 0.50. Specifically, it assumes hazard rates of 1.00 for the standard care group, versus 0.50 for the image guided group. Since the hazard rate is constant across months, this is equivalent to median survival times of 0.69 years for the standard treatment versus 1.39 years for the image guided intervention group.

The power analysis for the secondary outcome (clinical events) was based on the paper by Brown et al.²⁴ This paper reported mortality rates at 30 months in two treatment groups (2/48 = 0.042 and 3/46 = 0.065) and a control (10/52 = 0.192). We used these rates, as well as the combination for the two treatment groups (5/94 = 0.053). The calculation of power was based on the log-rank test⁽²⁵⁾ assuming a 24 month study. Using a twosided test at the 5% level of significance, we obtained the following results.

 			
Treatment	0.042	0.053	0.065
Mortality Rate			
Sample			
Size/group			
50	0.57	0.47	0.38
80	0.82	0.71	0.59
100	0.91	0.82	0.70

Power of the log-rank to detect the indicated difference from control

We assume that the attrition rate will be 0.20 in the 24-month follow-up. Thus, recruiting 200 study participants with 160 anticipated to complete 24 months of follow-up will be sufficient for this study.

Data Analysis:

1. The intent-to-treat and missing data:

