Standard statistical methods⁽²⁴⁾ will be used to describe the demographic characteristics, clinical manifestations and basic summary statistics as rates or means (medians). Confidence intervals will also be computed. If necessary, permutation methods⁽²⁶⁾ will be employed.

For Hypotheses 1, 2, and 4:

Linear mixed (random-effects) models⁽²⁷⁾ will be used to study differential changes over time in plaque size and composition and drug dosage between the two treatments. Each model will include main effects of time from baseline and treatment, with interactions tested separately. To decide on the correlation structure for these models, variation due to random effects, serial correlation and measurement error will be examined using the variogram. These models will also be used to isolate specific comparisons of outcome variables at specific time points between the two arms. The required assumptions of normally distributed errors and random effects can be checked by an analysis of standardized residuals. which are now available for the mixed model. In the event that the assumptions are not satisfied, usually because of skewed error distributions, data transformations from the Box-Cox power family will be considered. The most commonly used member of this family is the logarithmic transformation, which usually corrects a problem with right skewness.

For Hypothesis 3:

For the time-to-event data, both the Kaplan-Meier estimate and the Cox proportional hazards model will be employed. The primary analysis will compare the two treatments using a log-rank test. Secondary analyses will use the Cox model to include adjustment for covariates. A non-parametric proportional hazards model will also be used to explore possible transformations of independent variables in the models⁽²⁸⁾.

For Hypothesis 5, 6, and 7:

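### Section 6.0 powers the secondary event comparison on a 66–78% reduction, while section 7.4 expects 16–21% in intensified participants; at 16–21% and the plan's own 0.192 control rate, power is about 0.07–0.115

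*Combined protocol and SAP*

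**What the plan says.** The third aim in section 1.2 asks whether MRI-guided regression "produces greater reduction in clinical CV events than standard NCEP guided therapy". The matching endpoint in section 1.1 is secondary: "Combined incidence of stroke, nonfatal MI, myocardial revascularization, hospitalization for unstable angina or heart failure and death".

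Section 6.0 describes power for this comparison in two ways. One paragraph uses a hazard ratio of 0.50, with hazards of 1.00 and 0.50. The next takes rates from a cited coronary regression trial, labelled 30-month mortality: "two treatment groups (2/48 = 0.042 and 3/46 = 0.065" in the treated groups, "and a control (10/52 = 0.192" in the controls. A table of log-rank power (two-sided 5%, 24 months) follows. At 80 per group it shows 0.82, 0.71 and 0.59 for treated rates of 0.042, 0.053 and 0.065. After the attrition assumption the text concludes: "Thus, recruiting 200 study participants with 160 anticipated to complete 24 months of follow-up will be sufficient for this study".

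For Hypothesis 3 the same section states: "The primary analysis will compare the two treatments using a log-rank test". Cox models come second.

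Section 7.4 describes the benefit to participants as "intensification of statin therapy that would not otherwise be indicated in usual clinical care" and puts a size on it: "This carries the likelihood of significant reduction (16-21% relative risk reduction) of the risk of clinical cardiovascular events".

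**The concern.** The protocol expects one size of event benefit when it justifies the study to participants, and a far larger one when it reports power for the event comparison. The power table is the only quantitative support for Aim 3, and nothing in section 6.0 warns that a benefit of the size in section 7.4 would almost always be missed.

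The risk lies in the reporting. A non-significant log-rank, read next to a table of respectable power figures and a statement that 200 participants are enough, could be taken as evidence that image guidance does not affect events.

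This is separate from the disagreement within section 6.0 between the hazard ratio of 0.50 and the table's rates. Settling that disagreement either way still leaves an assumed reduction of at least 50%.

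**Working it through.** **Inputs.** From section 6.0: control rate 0.192; treated rates 0.042, 0.053 and 0.065; two-sided 5% log-rank; 24 months; 160 completers of 200 randomised, so 80 and 100 per arm at equal allocation; hazards 1.00 and 0.50. From section 7.4: relative reduction r = 16–21%.

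**1. Effect behind the table.** 1 − 0.042/0.192 = 78%; 1 − 0.053/0.192 = 72%; 1 − 0.065/0.192 = 66%. As hazard ratios, ln(1 − pT)/ln(1 − pC) gives 0.20, 0.26 and 0.32.

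**2. The plan's own figures.** At 80 per group:

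| Method | 0.042 | 0.053 | 0.065 |
|---|---|---|---|
| Stated in section 6.0 | 0.82 | 0.71 | 0.59 |
| Freedman formula, rates as given | 0.820 | 0.747 | 0.656 |
| Fisher exact, rates as given | 0.826 | 0.726 | 0.611 |
| Simulated log-rank, rates scaled to 24 months | 0.793 | 0.705 | 0.611 |

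No method tried matches all nine cells of the table within 0.02. Fisher exact comes closest, with a largest gap of about 0.03. The table is therefore roughly right for its inputs, and what follows does not depend on an exact match.

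**3. Power at 16–21%.** Treated rate pT = pC(1 − r); HR = ln(1 − pT)/ln(1 − pC); events D = n(pC + pT); power = Φ(½√D·|ln HR| − 1.96).

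For r = 16% and 80 per arm: pT = 0.192 × 0.84 = 0.161; HR = 0.825; D = 80 × 0.353 = 28.3; ½√28.3 × 0.192 = 0.51; Φ(0.51 − 1.96) = 0.074.

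For r = 21% and 80 per arm: pT = 0.152; HR = 0.772; D = 27.5; Φ(0.68 − 1.96) = 0.100.

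| Control assumption | Per arm | Events | Power at 16% | Power at 21% |
|---|---|---|---|---|
| 0.192 as given | 80 | about 28 | 0.074 | 0.100 |
| 0.192 as given | 100 | about 35 | 0.083 | 0.115 |
| Scaled to 24 months: 1 − 0.808^(24/30) = 0.157 | 80 | about 23 | 0.066 | 0.087 |
| Scaled to 24 months: 0.157 | 100 | about 28–29 | 0.073 | 0.099 |
| Hazard 1.00 per year, HR 0.84 or 0.79 | 80 | about 133–134 | 0.17 | 0.27 |
| Hazard 1.00 per year, HR 0.84 or 0.79 | 100 | about 166–168 | 0.20 | 0.33 |

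The hazard is read as per year because the stated medians of 0.69 and 1.39 years equal ln 2/1.00 and ln 2/0.50. Over two years it implies a control event rate of 1 − e^(−2) = 0.865.

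The Freedman formula agrees with the rate-based rows (0.192 and 0.157) to about 0.001. Simulated log-rank tests on those rates reject in 0.076–0.120 of trials. Reading 16–21% directly as a hazard reduction on those rates gives 0.062–0.103. The documents give no control rate for the composite; assuming 5% to 50% over follow-up, power runs from about 0.04 to 0.33.

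**4. Events needed for 80% power.** 4(1.96 + 0.842)²/(ln HR)² gives about 848 at HR 0.825 and 467 at HR 0.772.

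**5. What a null result could exclude.** The 95% interval around an observed hazard ratio of 1.0 is exp(±1.96 × 2/√D): 0.52–1.94 with 35 events, 0.48–2.10 with 28, and 0.44–2.29 with 22.5. Each contains 0.77–0.84, the hazard ratios that correspond to section 7.4.

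**The case against.** Several points on the other side are sound.

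- A reader might infer that the trial was sized on the event effect. It was not. Section 6.0 derives 80 per arm, and 200 with attrition, from a 40% versus 20% decrease in plaque volume, and first calls 200 enough in that context. The event table also openly shows 0.71 and 0.59 at 80 per group. What remains is that the claim is repeated, without limitation, directly after the event power table.
- A reader might infer that the two sections flatly contradict each other on one quantity. Section 7.4 describes individuals whose statin is intensified, not a predicted difference between arms. The outcome labels differ too: clinical cardiovascular events in one place, mortality in the other. This does not help power. Section 1.2 says imaging may reduce therapy as well as intensify it, so the effect across the whole arm could be smaller than 16–21%.
- The power figures join a reduction from one source to a control rate from another, and the protocol never states that combination. This is fair, and it is why a range is shown. No control rate tried gives adequate power.
- The plan already includes Kaplan-Meier estimates, a Cox model and confidence intervals, and nowhere says that non-significance will be read as no benefit. This is true, so the gap is a missing caveat rather than a missing analysis.
- Low power for a secondary event endpoint is common in a 200-patient imaging trial. It is acceptable when disclosed; here the stated figures point the other way.

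**Conclusion.** The point holds for the secondary event comparison only. Its stated power rests on a 66–78% reduction, or on a hazard ratio of 0.50, while the protocol elsewhere expects 16–21% in those whose therapy is intensified. At that effect, power is about 0.07–0.115 on the 0.192 rate as given, 0.07–0.10 with the rate scaled to 24 months, and 0.17–0.33 at a hazard of 1.00 per year.

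These figures assume that a 30-month rate labelled mortality can stand in for the composite, that hazards are constant and proportional, and that the whole image-guided arm receives the intensification benefit. The last assumption is generous.

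A reader might go further and say that a null result cannot be interpreted at all. The documents do not support that: a hazard ratio with its interval remains informative about large effects. The supportable statement is that, with about 22–35 events on the 0.192-based rates, non-significance could not exclude the benefit the protocol expects. Nor do the documents support replacing the prespecified log-rank at this stage, since section 7.4 records that the study moved to data analysis only in January 2017.

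**What to change.** In section 6.0, add power at a 16–21% reduction beside the event table, over a stated range of control rates, and say which rate is assumed for the composite and over what period. Confine the claim that 200 participants suffice to the primary wall-volume endpoint.

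For Hypothesis 3, keep the prespecified log-rank test. Report the Cox hazard ratio with its 95% confidence interval next to it, and state that a non-significant result is not evidence of no difference.

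Date and explain the change, because the study is in data analysis only. Enrol no more patients.

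The cost is wording and a less favourable stated power for a secondary aim. No new data, no change to the primary analysis and no change to patient management are involved.

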7.5 Consent Process and Documentation

Patients asked to participate in PET imaging will be consented separately for their participation in the main protocol and the substudy. Patients asked to participate in the Reproducibility Substudy will be consented separately for their participation in the main protocol and the substudy. The investigational nature

and objective of this trial, the procedures involved and their possible risk and discomforts, potential benefits, and possible alternative therapies will be explained to participants. The subject will be provided with a copy of the consent with enough time to review it and ask questions prior to the consent process. Participants will be enrolled after eligibility criteria have been determined and a signed informed consent document has been obtained. Consent for NIH employee will not be obtained from individuals in their supervisory chain of command.

The following investigators are authorized to obtain informed consent from the study subjects and are marked with an asterisk (*) on page 1 of the protocol:

```
- .
-
- .
- [name].
-
```

7.6 Data Safety and Monitoring

The entire study data set will be managed by the principal investigator. The entire data set will be contained in a secure database located on the NIH server. The forms to record data for this study will be generated and carefully reviewed for completeness, discrepant, inappropriate, and illogical responses. The data will checked for duplicate entries, with range checks on each field and consistency checks between fields with linked information. In cases of incoherent or missing data, the study coordinator will be immediately contacted and, if necessary, the form returned for CRF correction by the data manager. If multiple problems are found, a larger percentage of patient records will be audited. Non-image study data will be managed through the NICHD Clinical Trials Database system and stored on secure, redundant servers. Study image data will reside on the PACS.

A data safety and monitoring board will review all laboratory and safety data. At regular 6-month intervals the DSMB will monitor the safety and efficacy of image guided therapy compared with the standard therapy control arm. This will include evaluation of enrollment, compliance, follow-up, laboratory results, data management, and quality control. The DSMB will decide at each of these reviews whether the study will continue as originally designed. Efficacy analyses will be conducted for two interim analyses (at the end of year one and year two) and one final evaluation. The members of the DSMB, pending acceptance, will be [name] (Northwestern University, Chicago) – biostatistics and epidemiology; [name] (University of Pennsylvania) – cardiology and cardiovascular imaging, and [name] (University of Maryland)—general cardiology.

Data confidentiality:

Patient image data will be maintained on PACS database systems within the Department of Radiology with security and redundancy at the level of the clinical PACS system used by the NIH clinical center The confidentiality and security of the data files containing PHI will be maintained by ensuring password protection on all computer accounts. Protection against loss of data is essential to our data management. Copies of the study database files will reside in an independent backup hard drive.

Data reporting will be done through presenting in national meetings and publishing in journals.

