6.0 Statistical Section

Data from the recently concluded NIA Plaque Study, a randomized double-blind trial of the effect of niacin vs. placebo on MRI plaque volumes were collected on 145 subjects at baseline, and at 18-month follow-up. For the primary endpoint in the proposed study, carotid wall volume, the standard deviation of the differences between 18 months and baseline was 125 mm³, combining data from both the left and right arteries. The baseline mean for the entire group was 300.0. Since the proposed study has a longer duration (24 months) than the NIA Plague Study, and since we have the benefit of improvements in MRI technology, we anticipate a larger effect size than was seen in the NIA Plague Study. The sample size calculations were based on finding a 40% decrease in plaque volume in the image-guided arm compared to a 20% decrease in the conventional treatment arm at 24 months using a two-sample t-test. The table below shows the power to detect this difference at the 5% level of significance, assuming 80 subjects in each group. These power calculations were based on comparing the change from baseline at a single time point. However, the primary analysis will employ a mixed model, which will include multiple observations per patient. Therefore, 80 patients in each group will certainly provide adequate power. As discussed below we assume that the attrition rate will be 0.20 at the 24-month follow-up. Thus, recruiting 200 study participants will be sufficient for this study. These calculations were based on the optimal allocation of equal numbers to the two arms. However a 3/1 ratio of image-guided to conventional therapy did not meaningfully reduce the power.

		Decrease in Plaque Volume (Control Art		
Decrease in		15%	20%	25%
plaque volume	35%	0.85	0.62	0.33
(Image guided	40%	0.96	0.85	0.62
arm)	45%	0.99	0.96	0.85

Power of a two-sample t test to detect the indicated difference in change from baseline at 24 months

For the secondary end-point of this study, the task is to test the null hypothesis that the hazard rate, which is assumed to be constant across all study months, is identical in the two groups (image guided vs.

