The intent-to-treat (ITT) approach will be used for the primary analysis. According to this generally recommended approach, comparisons are made according to randomized treatment assignment, regardless of any changes in dose, schedule or treatment arm. In an ITT analysis, all randomized study participants are included in their assigned treatment groups, regardless of compliance with the assigned treatment regimen. On the other hand, the weakness of ITT is that it assesses the effect of treatment for subjects known not to have used the treatment enough to have any effect. While conventional ITT will be the method used to analyze and report the primary results, in order to derive valid estimates of treatment effect accounting for compliance with therapy, model-based analytical methods will also be employed, and non-ITT analysis will be performed.

In fact, in the present study, we do not foresee noncompliance as a problem since treatment administration is under the control of the study physician rather than the patient. Dropout, however, is always a potential problem. In this study we have assumed a dropout rate of 20%, since we anticipate a lower dropout rate than the 25% in the previous trial. This is because we are using three scans over two years rather than four over 18 months as in the previous study, and many of the previous dropouts were related to MRI anxiety. Thus we do not anticipate problems with differential dropout. In addition, approximately one-third of the dropouts in the previous study were due to problems with niacin flushing, which again will not be a problem in the present study.

2. Multiple outcome measures:

In this clinical trial, we will evaluate multiple outcome measures: changes in plaque architecture and composition measured by MRI, and time to events, including the incidence of cardiovascular and cerebrovascular outcomes and disease-specific death. The following approaches to evaluate multiple outcome measures will be implemented: (i) defining a primary outcome measure; (ii) correcting for multiple testing, such as Bonferroni adjustment; (iii) with data on major clinical events, adopting a combined endpoint, such as time to first cardiovascular event or death, whichever occurs first.

3. Data Analysis:

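### Two interim efficacy analyses are planned with no endpoint, clock, boundary or alpha; define them in the plan, and state in the report whether any look was taken and under what rule.

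*Combined protocol and SAP*

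**What the plan says.** Section 7.6 (Data Safety and Monitoring) sets out two layers of efficacy review.

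- Six-monthly reviews: "At regular 6-month intervals the DSMB will monitor the safety and efficacy of image guided therapy compared with the standard therapy control arm". On these it adds "The DSMB will decide at each of these reviews whether the study will continue as originally designed".
- Two interims and a final: "Efficacy analyses will be conducted for two interim analyses (at the end of year one and year two) and one final evaluation".

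It does not say which endpoint is examined, from when the years are counted, what test or boundary applies, or how the two interims relate to the six-monthly reviews.

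Section 6.0 does not mention interim analysis. For the primary endpoint it states "The table below shows the power to detect this difference at the 5% level of significance, assuming 80 subjects in each group", based on the change at a single time point, 24 months. It then says "However, the primary analysis will employ a mixed model, which will include multiple observations per patient". For clinical events it states "Using a twosided test at the 5% level of significance, we obtained the following results". Its multiplicity text reads "approaches to evaluate multiple outcome measures will be implemented: (i) defining a primary outcome measure; (ii) correcting for multiple testing, such as Bonferroni adjustment", which concerns several endpoints rather than several looks at one.

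On timing, section 6.0 says "The study design calls for an accrual period of 50 months and a follow-up period of 24 months". Section 3.1 expects 3-4 participants a month. Section 1.3 schedules carotid MRI at baseline, 12 and 24 months, and section 3.2 allows 30 days either side of a visit. Section 7.4 records that the study has been in its analysis phase only since January 2017.

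**The concern.** Three efficacy analyses with no boundary do not secure the 5% level that section 6.0 relies on. A board that compares the arms and can decide on continuation may act on a chance difference, and each further test at 5% adds to the overall false-positive rate.

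The schedule also fits the powered endpoint poorly. A look needs 24-month scans to inform the 24-month contrast, and with slow accrual few or none exist at the times that the words most naturally suggest. Someone reading the final p-value therefore cannot tell how many tests lie behind it, on what data, or whether 5% is the right benchmark.

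**Working it through.** **1. The plan's own figure.** Inputs from section 6.0: baseline mean 300, SD of change 125, decreases of 40% and 20%, 80 per arm.
- Difference = 0.20 × 300 = 60 mm³.
- Noncentrality = 60 / (125 × √(2/80)) = 3.036.
- Two-sided 5% t-test on 158 df: power 0.855, against 0.85 in the table.

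The table is reproduced as one two-sided test at 5%, with nothing set aside for interim looks.

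**2. Data available at each look on the 24-month endpoint.**

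| Clock | Year one | Year two |
|---|---|---|
| Calendar, from study start | 12×3=36 to 12×4=48 enrolled; no 24-month MRI | 72-96 enrolled; 36-48 with a 12-month MRI due; at most 3-4 with a 24-month MRI, using the 30-day window |
| Participant follow-up | 12-month MRI only | 24-month MRI, which is the final analysis |
| After accrual closes (4 a month, month 50) | Month 62: 4×(62−24)=152, or 156 with the window, of 200 (76-78%) | Month 74: all 200, which is the final analysis |

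Only 4 a month fills 200 places in 50 months (200/4 = 50; 200/3 = 67). No row gives two separate interim looks plus a final on the 24-month contrast. The third row gives one.

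**3. Type I error if a look is tested at two-sided 5% with power to stop or claim.** For one interim at information fraction f, the interim and final z-statistics are bivariate normal with correlation √f. Overall error = 1 − P(|Z₁|<1.96 and |Z₂|<1.96).

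*24-month contrast, one look a year after accrual closes.* f = 0.76-0.78 gives 7.3-7.2%.

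*Mixed model.* The documents give only an 18-month SD, so these inputs are assumptions:
- SD of 24-month change 125; SD of 12-month change s = 90-125.
- Correlation of the two changes 0.5-0.7.
- Effect at 12 months a = 0.5 (linear in time) or 1 (constant), relative to 24 months.
- 160 completers.

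With V the covariance of the two changes and d = (a, 1), f = (n/160) × (a²/s²) / (d′V⁻¹d), where n is the number with a 12-month change at the look.
- Calendar month 24, n = 36-48: f = 0.052-0.300, error 9.6-8.9%.
- Participant year one, n = 160: f = 0.232-0.999, error 9.1-5.1%.

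*Clinical events.* Log-rank tests simulated under the null at calendar months 12 and 24 and at the end; 200 patients, 3 or 4 a month, 24 months of follow-up each. Section 6.0 gives two inconsistent sets of event rates, so both are shown.
- 30-month rates: 0.192 (control), or 0.1225 = (0.192+0.053)/2. Annual hazards −ln(1−0.192)/2.5 = 0.085 and −ln(1−0.1225)/2.5 = 0.052; attrition 0 or 20%. About 1-2 events at month 12, 3-8 at month 24 and 18-31 at the end. Overall error about 8-10%.
- Annual hazards 0.50-1.00, attrition 20%: about 8-17 events at month 12 and 25-52 at month 24. Overall error about 12-13.5%.

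**4. Two candidate repairs.**
- p<0.001 at an interim, final at 5%: overall 5.0-5.1% for the mixed model, 5.0% for the look a year after accrual closes, and 4.8-5.0% (simulated) for events at the 30-month rates.
- An interim already tested at 5%, with only the final level lowered: final 0.0256 at f = 0.05 leaves 7.3%, and 0.0274 at f = 0.30 leaves 7.0%. These are the levels that would have held 5% had both looks used them. The interim has already spent the full 5%, so lowering the final level afterwards cannot recover it.

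**The case against.** The strongest reply is that nothing in the documents says a 5% test was made at any look. The continuation decision is attached to the six-monthly reviews, whose listed content is enrolment, compliance, follow-up, laboratory results, data management and quality control. No sentence gives the two interims power to stop or to claim efficacy. All of that stands, and it makes every inflation figure conditional.

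Three stronger readings are tempting and are not supported:

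- A reader might infer that the trial's error rate was in fact inflated. The documents do not say whether any look was taken.
- A reader might infer that the interim schedule is unworkable altogether. It fails only as two looks at the 24-month contrast. For events, calendar months 12 and 24 and the end are three distinct looks, although at the 30-month rates the first holds only 1-2 events. A mixed-model look on 12-month MRI is also possible.
- A reader might treat the six-monthly reviews as about 12 formal tests over 74 months. Equally spaced and unadjusted at 5%, these would give about 21%, but no passage describes those reviews as hypothesis tests.

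The mixed-model range does rest on assumed 12-month inputs, and for a participant year-one look (5-9%) it says only that inflation could be slight or material. It is also fair that a boundary can no longer be set prospectively.

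**Conclusion.** The gap is real: efficacy looks are planned, and the text that should protect the 5% level is absent. For the powered 24-month contrast, two distinct interims plus a final cannot be had on any of the three clocks.

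The size depends on facts that the documents do not give. Provided looks were tested at an unadjusted two-sided 5% with power to stop or claim, overall error is:

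- about 9-10% for the mixed model with one calendar month-24 look;
- about 5-9% for the mixed model with a participant year-one look;
- about 7% for the 24-month contrast with one look a year after accrual closes;
- about 8-10% for events at the 30-month rates, or 12-13.5% at hazards of 0.50-1.00.

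It is 5% if no look was tested. It is also 5% for a pure 24-month contrast if the only looks held no 24-month data. This should be fixed, but it does not show that the final result is unsound.

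**What to change.** **In the plan text.** Name the endpoint and analysis for each interim, say from when the years are counted, and say how the interims relate to the six-monthly DSMB reviews. Then either state that interim efficacy reviews are descriptive, or use p<0.001 (Haybittle-Peto) at interims with the final test kept at 5%. The final test is unchanged, so there is essentially no power cost (0.855 at 80 per arm). The price is one paragraph.

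**Still open, in the final report.** With the study in data analysis only, a prospective rule can no longer be adopted. The report should state whether any between-arm efficacy look was taken, including at six-monthly reviews, on which endpoint and data, and under what rule.

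- If none was tested, keep 5% and say so.
- If one was tested at 5% with power to stop or claim, report the resulting overall error beside the final p-value. Do not present a lowered final threshold as restoring 5%.

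This costs one statement, drawn from the DSMB records.
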